#### 3.6.1. Interventions, Observations, or Data Sought:

**Procedure:** Interested individuals will be directed from our recruitment materials (e.g., posters, flyers, business cards, listservs, and electronic media) to visit the study recruitment office (located in the obstetric clinics) to learn more and determine whether they meet the eligibility criteria. If, after learning more about the study, individuals continue to be interested, written informed consent will be obtained and measures will be administered. The potential participant will also be asked to complete a one-week dietary and exercise self-monitoring run-in, turn in a copy of their fitness scores to study staff (if active duty), and receive medical clearance from their obstetrician to participate. (Note: In the unfortunate event that a potential participant miscarries before being randomized, she will have the opportunity to re-screen if she chooses.) Should she continue to be interested, she will return for a Baseline Visit and will be randomized to 1 of 3 conditions: a) GWG-only; b) PPWL-only; or c) GWG+PPWL and oriented to the assigned treatment condition.

**Randomization:** Participants (n=450) will be randomly allocated to 1 of the 3 conditions, using a computer algorithm under the direction of the study biostatistician, [name], with a sequence blocked by screening BMI category (i.e., normal weight, overweight, obese) in order to ensure equal distribution by condition with respect to BMI category. Each condition will have the same number of subjects.

**Intervention Overview:** The novel stepped-care behavioral GWG and/or PPWL intervention--designed to assist participants meet the Institute of Medicine (IOM)-recommended GWG guidelines and produce PPWL--will be based on the Look AHEAD Intensive Lifestyle Intervention. The Look AHEAD Intensive Lifestyle Intervention methods are consistent with those utilized in previous studies of effective approaches to producing appropriate GWG and PPWL. However, the Look AHEAD approach offers greater structure and support than some of the methods used in previous work. We will also tailor our intervention to the military lifestyle (e.g., managing stressors such as increases in dietary intake, reduced physical activity related to spouse deployment, environmental facilitators such as access to the free fitness centers). We have previously tailored our interventions to the military lifestyle and environment, and our programs have been extremely well received by military personnel.

**GWG Intervention:** The GWG intervention will begin upon randomization to the GWG-only or the GWG+PPWL arm, and continue until the birth of the participant’s child. This intervention will provide individual, telephone-based sessions (20-30 minutes each), as detailed in Table 1, by trained interventionists. The number of possible telephone sessions will depend on the gestational age at randomization and the level of support needed by the participant to meet the IOM guidelines. The intervention will focus on self-monitoring, clear goals (i.e., GWG, caloric intake exercise), and problem solving.

**Table 1. Stepped-Care Gestational Weight Gain Intervention**

	Step 1	Step 2	Step 3
Trigger to Increase Intervention Intensity	- >0.5 lb above GWG guidelines at any monthly session	- >0.5 lb above GWG guidelines for 2 consecutive biweekly sessions	-N/A
Contact Frequency	-Monthly 20-30 minute telephone session	-Biweekly 20-30 minute telephone session	-Weekly 20-30 minute telephone session - Weekly emailed materials
Dietary Recommendations	1st trimester: Maintain 2nd trimester: ↑ by 340 calories per day 3rd trimester: ↑ by 452 calories per day	Same as Step 1 with portion size measuring and daily dietary intake monitoring	↓ by 100-200 calories per day until appropriate GWG achieved
Exercise	-150 minutes per week of moderate activity -Fitness tracker	-150 minutes per week of moderate activity -Fitness tracker	-150 minutes per week of moderate activity -Fitness tracker
Behavioral Strategies	-Weekly self monitoring of weight -Weekly emailed graph	-Daily self monitoring of weight, daily food intake & exercise -Weekly emailed graph -Goal setting & problem solving	-Daily self monitoring of weight, daily food intake & exercise -Weekly emailed graph -Goal setting & problem solving -Meal replacements & structured meal plans - Adapted Look AHEAD ILI lesson materials -Toolbox resources
Trigger to Reduce Intervention Intensity	N/A	Return to GWG within the IOM guidelines	Return to GWG within the IOM guidelines

Being above the GWG recommendations will trigger an increase in the intervention intensity (i.e., moving to the next step—so gaining more weight at any monthly telephone session for those in Step 1 will trigger an increase in the intervention intensity (i.e., moving to Step 2), and any participant in Step 2 who is above the line for 2 consecutive biweekly sessions will trigger an increase in the intervention intensity (i.e., moving to Step 3). This stepped-care approach will have optimal translation to the practice setting, because it allows targeted allocation of resources. Further, this approach allows greatest tailoring of the intervention intensity to the individual (those who have trouble staying within the guidelines early in pregnancy will get more assistance at that time, with a decrease in intervention intensity when their GWG is within the recommended range; those who stay within guidelines early on but require assistance maintaining adherence with guidelines later in their pregnancy receive assistance when they start to experience challenges). A similar stepped-care approach, designed by [name], has been well received by pregnant women in the “Glowing” study.

**Weight goals:** The GWG goals for each participant will reflect the 2009 IOM guidelines[30]: a) for normal weight women (BMI 18.5-24.9 kg/m^2): 11-16 kgs (25-35 lbs); b) for overweight women (BMI 25.0-29.9 kg/m^2): 7-11.5 kgs (15-25 lbs); and c) for obese women (BMI 30-39.9 kg/m^2): 5-9 kgs (11-20 lbs) based on their weight collected at their screening appointments. Ongoing weight self-monitoring will be a central feature of the intervention at all steps. Most experts considered frequent weighing a key component to any weight management program (83-86) and it appears to be important in pregnancy-related weight interventions as well. For this reason, participants will be prompted to weigh themselves at least weekly on an electronic scale, which they will be given at baseline. The electronic scale will be issued to the subject as part of treatment on a hand receipt. Due to depreciation of the scale over 21 months of use during the study, the scales would be valued at near zero, and therefore subjects will not be required to return them. The electronic scales are part of the treatment and not considered a form of compensation for participating in the study. Each time a participant weighs, the electronic scale will upload the weight automatically to a secure website. Each week, participants will receive an email from their interventionist with a weight graph tailored to their screening weight BMI and their current weight trajectory as well as personalized feedback from their interventionist about their trajectory. Participants who gain less weight than the guidelines will be instructed to increase their caloric intake and to monitor their weight daily. Study staff will notify Obstetrics staff about participants who gain less weight than the guidelines at two consecutive intervention sessions, but will be retained in the study.

**Dietary goals:** Consistent with the IOM recommendations[30], participants will be advised to continue consuming the same number of calories in the first trimester as they did pre-pregnancy, and increase baseline intake (if they are otherwise meeting their GWG goals) by approximately 340 calories in the second trimester, and by 452 calories in the third trimester. Participants will be given examples of 350 and 450 calories of food, in order to guide adherence with these goals. Other dietary recommendations will be consistent with a “healthy” diet for pregnant women (e.g., limiting fish consumption), with an emphasis on consuming a diet high in fruits, vegetables, and whole grains. We will pair self-monitoring, with instructions in food label reading and measuring foods to improve self-monitoring accuracy. However, among women who are gaining in excess of the guidelines who have self-reported calorie intakes within the specified goal ranges, recommendations for decreases in the calorie goals will be made; this is predicated on the assumption that the actual energy intake is higher than the self-reported intake and that lowering the goal for self-reported intake will achieve an intake level that supports appropriate GWG.

**Exercise goals:** Participants will be encouraged to engage in 150 minutes per week of moderate exercise. Fitness trackers will be issued with a hand receipt to participants as part of treatment to facilitate reaching their exercise goal. The fitness trackers are part of the treatment and not considered a form of compensation for participating in the study. After 21 months of use, the value of the fitness tracker will be near zero due to depreciation and advances in technology; therefore, participants will not be asked to return the fitness trackers. If the participant’s obstetrician recommends limiting physical activity or complete bed rest, the exercise goal will be modified or halted.

**PPWL Intervention:** The PPWL intervention will begin at 6-weeks postpartum (when most women will be approved for weight loss and exercise by their obstetrician) for those participants randomized to the PPWL-only or the GWG+PPWL arms, and will continue until 12-months postpartum. The PPWL intervention will provide at least monthly individual, telephone-based sessions (20-30 minutes each), as detailed in Table 2, by trained interventionists. (The number of possible telephone sessions will depend on the level of support needed by each participant to meet her weight loss goals). Similar to the GWG intervention, the PPWL intervention will focus on self-monitoring; weight, dietary intake and exercise goals; and problem solving.

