**Table 2. Stepped-Care Postpartum Weight Loss Intervention**

	Step 1	Step 2	Step 3
Trigger to Increase Intervention Intensity	<0.5-1 lb of weight loss per week at any monthly session	<0.5-1 lb of weight loss per week for 2 consecutive biweekly sessions	N/A
Contact Frequency	-Monthly 20-30 minute telephone sessions	-Biweekly 20-30 minute telephone sessions	-Weekly 20-30 minute telephone sessions -Weekly emailed materials
Dietary Recommendations	500 calorie deficit, tailored to breastfeeding status	Same as Step 1 with portion size measuring and daily dietary intake monitoring	↓ by 100-200 calorie per day until recommended weight loss achieved
Exercise	-↑ exercise to pregravid levels -Fitness tracker	-↑ exercise to pregravid levels -Fitness tracker	-↑ exercise to pregravid levels -Fitness tracker
Behavioral Strategies	-Weekly self monitoring of weight -Weekly emailed graph	-Daily self monitoring of weight, daily food intake & exercise -Weekly emailed graph -Goal setting and problem solving	-Daily self monitoring of weight, daily food intake & exercise -Weekly emailed graph -Goal setting & problem solving -Meal replacements & structured meal plans - Adapted Look AHEAD ILI materials -Toolbox resources
Trigger to Reduce Intervention Intensity	N/A	Return to weight loss within recommended range	Return to weight loss within recommended range

Failure to lose weight based on the expected trajectory (i.e., 1 lb per week until returning to their pregravid weight (for women who are in any pregravid weight category) or until they have achieved a 5% weight loss (for overweight and obese women, if they desire)) will trigger an increase in the intervention intensity (i.e., moving to the next step). That is, failure to lose weight based on the expected trajectory at any monthly session for those in Step 1 will trigger an increase in the intervention intensity (i.e., moving to Step 2) and any participant in Step 2 who is losing less than the expected trajectory for two consecutive biweekly sessions will trigger an increase in the intervention intensity (i.e., move to Step 3).

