**Dietary goals:** Calorie goals will be based on their baseline caloric intake and their current breastfeeding status. Women who are breastfeeding will be given a calorie goal that allows for the additional energy expenditure of breastfeeding (i.e., an extra 450-500 calories). While the primary emphasis will be to stay within the prescribed goal, participants will be also encouraged to eat a balanced diet in line with the current U.S. Dietary Guidelines. Among women who are not losing weight at the expected rate who have self-reported calorie intakes within the specified goal ranges, decreases in their calorie goal will be made; this is predicated on the assumption that the actual energy intake is higher than the self-reported intake and that lowering the goal for self-reported intake will achieve an intake level that supports appropriate weight loss.

**Exercise goals:** When approved by their obstetrician, participants will be encouraged to gradually resume their pregravid levels of exercise. Participants will be advised to set an initial exercise goal of 100 minutes per week and gradually increase the amount of moderate exercise that they perform. Fitness trackers will be issued with a hand receipt to participants as part of treatment to facilitate the exercise goal. After 21 months, the value of the fitness tracker will be near zero due to depreciation and advances in technology; therefore, participants will not be asked to return the fitness trackers. The electronic scales are part of the treatment and not considered a form of compensation for participating in the study. If the participant's obstetrician recommends limiting physical activity, the exercise goal will be modified or halted. Participants will also receive guidance about their ability to resume strength training (e.g., push-ups, sit-ups) at their first (i.e., 6-weeks) postpartum visit with their obstetrician, consistent with standard clinic practice.

**Common Intervention Components for the GWG and the PPWL Interventions:** In both interventions, participants will be taught behavioral techniques, as needed, to assist them in meeting their weight, calorie, and exercise goals.

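### Table 1 and the dietary-goals text give conflicting calorie rules for Step 2 women above the GWG guideline, and both tables omit the text's condition on the Step 3 decrease

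*Combined protocol and SAP*

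**What the plan says.** Section 3.6.1 of the combined protocol and SAP sets the calorie goals of each intervention twice, once in a table and once in a Dietary goals paragraph.

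**GWG, Table 1.** At Step 1, intake is maintained in the first trimester, raised "by 340 calories per day" in the second and raised "by 452 calories per day" in the third. Step 2 reads "Same as Step 1 with portion size measuring and daily dietary intake monitoring". Step 3 is a decrease, "by 100-200 calories per day until appropriate GWG achieved". None of these cells depends on reported intake, and the Step 1 and Step 2 cells do not depend on weight gain. A woman moves to Step 2 when she is more than 0.5 lb above the guideline at a monthly session. She moves to Step 3 when that holds at two biweekly sessions in a row, and she steps down once she is back within the guideline.

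**GWG, Dietary goals paragraph.** Women are to "increase baseline intake (if they are otherwise meeting their GWG goals) by approximately 340 calories in the second trimester", and by 452 in the third. Calorie goals are then lowered for "women who are gaining in excess of the guidelines who have self-reported calorie intakes within the specified goal ranges". That clause names neither a step nor an amount.

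**Postpartum weight loss (PPWL).** Table 2 gives Step 3 a decrease, "by 100-200 calorie per day until recommended weight loss achieved", with no condition on reported intake. The matching Dietary goals paragraph limits the decrease: "Among women who are not losing weight at the expected rate who have self-reported calorie intakes within the specified goal ranges".

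**The concern.** The woman affected at Step 2 is one whose gain is above the guideline, since that is what moved her up from Step 1. The table tells the interventionist to keep the trimester increase. The text grants that increase only when GWG goals are being met, and it lowers the goal for an over-gainer who reports intake within goal. Whatever she reports, the text does not support the table's entry in the second and third trimesters:

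- If her reported intake is within goal, the text lowers the goal and the table holds it.
- If her reported intake is above goal, the decrease clause does not apply, but neither does the condition for the increase.

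At Step 3 the disagreement is narrower. It concerns who receives the decrease, not its direction.

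What is at stake is the treatment delivered. Two interventionists working from different parts of the same section could give the same pregnant woman different calorie goals. Over-gaining is not expected to be rare: the background in sections 3.3 to 3.5 cites 53-71% of normal weight, 77-84% of overweight and 74-83% of obese women exceeding the guidelines.

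**Working it through.** The plan states no figure for this discrepancy, so there is none to reproduce. The increments themselves (340 and 452) agree between Table 1 and the text. What differs is who receives them.

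**Inputs**, as daily change from baseline intake:
- Table 1, Steps 1 and 2: 0, +340 and +452 in trimesters 1, 2 and 3.
- Table 1, Step 3: a decrease of 100 to 200, with no starting level named.
- GWG Dietary goals paragraph: the same increments, only for women otherwise on goal; a decrease of unstated size for over-gainers reporting intake within goal.

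**Step 2, woman above the guideline.** The text gives no explicit goal for her, so two readings are needed.
- *Reading A:* the condition fails, so she gets no increase. Gap = table increment − 0.
- *Reading B:* the decrease clause applies and its amount is the Step 3 figure, taken from the goal (assumed). Her goal is the increment less 200 to the increment less 100. Gap = 100 to 200.

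| Trimester | Table 1, Step 2 | Text, A | Gap A | Text, B | Gap B |
|---|---|---|---|---|---|
| 1 | 0 | 0 | 0 | −200 to −100 | 100 to 200 |
| 2 | +340 | 0 | 340 | 340 − 200 = +140 to 340 − 100 = +240 | 100 to 200 |
| 3 | +452 | 0 | 452 | 452 − 200 = +252 to 452 − 100 = +352 | 100 to 200 |

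In trimesters 2 and 3 neither reading returns the table's value.

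**Step 3, eligibility.** If reported intake is within goal, table and text both decrease. If it is above goal, Table 1 decreases by 100 to 200 and the text's decrease clause does not apply. If the goal would otherwise stay where it was (an assumption), the two differ by 100 to 200 calories a day. Table 2 and the PPWL paragraph differ in the same way and by the same amount.

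**Step 3, starting level.** Taken from the trimester goal, the Table 1 decrease leaves +140 to +240 (trimester 2) or +252 to +352 (trimester 3). Taken from baseline intake, it leaves −200 to −100. For the same size of cut these differ by 340 or 452. The GWG paragraph says that the calorie goal is what is lowered, which favours the first. This is an ambiguity inside one table cell, not a conflict between table and text.

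**The case against.** The strongest reply is that the table summarises a sequence that the text fills in. Daily food-intake monitoring starts at Step 2, and the decrease follows at Step 3 if over-gain persists. The text's decrease depends on self-reported intake, which that monitoring supplies. On this view the Step 3 cells merely omit a condition. That is fair for Step 3, where direction and target agree. It does not rescue Step 2: the table retains the increase for women whom the text's condition excludes, and the decrease clause is not confined to Step 3.

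A second reply is that interventionists will work from a detailed manual. Treatment Fidelity in section 3.6.1 lists detailed intervention protocol development, and weekly meetings review adherence. The manual is not in the documents and may settle the matter in practice. For that reason the documents do not support the inference that the recorded sessions have no standard to be judged against. The protocol's own statements should still agree.

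A third reply is that the primary analysis in section 6.3 is intention-to-treat regardless of adherence. That stands: endpoints, randomisation and sample size are unaffected.

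A reader might also object that the reference intake is undefined, because the GWG paragraph moves from pre-pregnancy to baseline intake and section 3.6.5 lists no dietary measure. This is weak. First-trimester advice is to leave intake unchanged, so the two are meant to coincide. The section 3.6.5 list also omits accelerometry, which section 3.6.8 collects. The one-week run-in gives a dietary record before the Baseline Visit, and intake is recorded later by website or app.

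**Conclusion.** The Step 2 conflict is real: as written, one stated rule contradicts another for women above the guideline. Its size is not fixed by the documents. It is 340 (second trimester) or 452 (third) calories a day if such a woman gets no increase, with no gap in the first trimester. It is 100 to 200 if the decrease clause applies at the Step 3 amount. Both are readings, because the text never states her goal.

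A reader might infer a documented gap of 340 to 452 calories a day across Steps 2 and 3. The documents do not support that. The two numbers are trimester-specific values on one reading, not a range. At Step 3 table and text agree on a decrease, and the text points to the calorie goal as its starting level. What remains there is the condition on reported intake that both tables omit, and a starting level that Table 1 should name.

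Nor do the documents show that calories are the main lever of the interventions or that over-gainers drive the Hypothesis 1 comparison. The point concerns the consistency of the delivered intervention. It is worth correcting because it bears on the goal given to pregnant women and is cheap to settle.

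**What to change.** Reconcile Table 1 with the GWG Dietary goals paragraph, and Table 2 with the PPWL one:

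- Give the same calorie rule in Table 1 and the GWG text for a woman in Step 2 who is above the guideline.
- State, in both tables and both paragraphs, whether the Step 3 decrease depends on reported intake being within goal.
- Name in Table 1 the level from which the Step 3 decrease is taken.

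Which rule applies is for the sponsor's obstetric and dietetic staff to decide; this review proposes none. The cost is a protocol wording amendment and an updated interventionist sheet. No new visits, data or analyses are needed.

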**Table 2. Stepped-Care Postpartum Weight Loss Intervention**

	Step 1	Step 2	Step 3
Trigger to Increase Intervention Intensity	<0.5-1 lb of weight loss per week at any monthly session	<0.5-1 lb of weight loss per week for 2 consecutive biweekly sessions	N/A
Contact Frequency	-Monthly 20-30 minute telephone sessions	-Biweekly 20-30 minute telephone sessions	-Weekly 20-30 minute telephone sessions -Weekly emailed materials
Dietary Recommendations	500 calorie deficit, tailored to breastfeeding status	Same as Step 1 with portion size measuring and daily dietary intake monitoring	↓ by 100-200 calorie per day until recommended weight loss achieved
Exercise	-↑ exercise to pregravid levels -Fitness tracker	-↑ exercise to pregravid levels -Fitness tracker	-↑ exercise to pregravid levels -Fitness tracker
Behavioral Strategies	-Weekly self monitoring of weight -Weekly emailed graph	-Daily self monitoring of weight, daily food intake & exercise -Weekly emailed graph -Goal setting and problem solving	-Daily self monitoring of weight, daily food intake & exercise -Weekly emailed graph -Goal setting & problem solving -Meal replacements & structured meal plans - Adapted Look AHEAD ILI materials -Toolbox resources
Trigger to Reduce Intervention Intensity	N/A	Return to weight loss within recommended range	Return to weight loss within recommended range

Failure to lose weight based on the expected trajectory (i.e., 1 lb per week until returning to their pregravid weight (for women who are in any pregravid weight category) or until they have achieved a 5% weight loss (for overweight and obese women, if they desire)) will trigger an increase in the intervention intensity (i.e., moving to the next step). That is, failure to lose weight based on the expected trajectory at any monthly session for those in Step 1 will trigger an increase in the intervention intensity (i.e., moving to Step 2) and any participant in Step 2 who is losing less than the expected trajectory for two consecutive biweekly sessions will trigger an increase in the intervention intensity (i.e., move to Step 3).

**Weight goals:** Weight loss from birth to 6-weeks postpartum is fairly standard—approximately 6 kilograms (or 13 pounds)—regardless of pregravid weight category and GWG [29]. For women with a normal pregravid BMI, the PPWL goal (initiated at 6-weeks postpartum) will be to return to the pregravid weight. For women who were overweight or obese pre-pregnancy, the PPWL goal (initiated at 6-weeks postpartum) will be to at least return to their pregravid weight and, if desired, lose up to an additional 5% of their pregravid weight. All participants will be advised to lose weight at a rate of approximately 1 pound per week, which has been shown to not have adverse effects on infant growth or breast milk production. All women will be given a tailored graph indicating the recommended PPWL trajectory. They will be prompted to weigh themselves at least weekly on the electronic scale provided at baseline (which will upload the weight automatically to a secure website). The electronic scale will be issued to the subject as part of treatment on a hand receipt. Due to depreciation of the scale over 21 months of use during the study, the scales would be valued at near zero, and therefore subjects will not be required to return them. The electronic scales are part of the treatment and not considered a form of compensation for participating in the study. These weights will be plotted on a graph and emailed to them weekly along

with personalized feedback from their interventionist about their weight trajectory. The graph will clearly identify weight losses that are both greater than recommended and below recommendations. Participants who are losing weight faster than expected will be instructed to increase their caloric intake and to monitor their weight daily. Participants who lose more weight than expected at 2 consecutive monthly intervention sessions will be referred to their obstetrician for guidance, but will be retained in the study.

**Dietary goals:** Calorie goals will be based on their baseline caloric intake and their current breastfeeding status. Women who are breastfeeding will be given a calorie goal that allows for the additional energy expenditure of breastfeeding (i.e., an extra 450-500 calories). While the primary emphasis will be to stay within the prescribed goal, participants will be also encouraged to eat a balanced diet in line with the current U.S. Dietary Guidelines. Among women who are not losing weight at the expected rate who have self-reported calorie intakes within the specified goal ranges, decreases in their calorie goal will be made; this is predicated on the assumption that the actual energy intake is higher than the self-reported intake and that lowering the goal for self-reported intake will achieve an intake level that supports appropriate weight loss.

**Exercise goals:** When approved by their obstetrician, participants will be encouraged to gradually resume their pregravid levels of exercise. Participants will be advised to set an initial exercise goal of 100 minutes per week and gradually increase the amount of moderate exercise that they perform. Fitness trackers will be issued with a hand receipt to participants as part of treatment to facilitate the exercise goal. After 21 months, the value of the fitness tracker will be near zero due to depreciation and advances in technology; therefore, participants will not be asked to return the fitness trackers. The electronic scales are part of the treatment and not considered a form of compensation for participating in the study. If the participant's obstetrician recommends limiting physical activity, the exercise goal will be modified or halted. Participants will also receive guidance about their ability to resume strength training (e.g., push-ups, sit-ups) at their first (i.e., 6-weeks) postpartum visit with their obstetrician, consistent with standard clinic practice.

**Common Intervention Components for the GWG and the PPWL Interventions:** In both interventions, participants will be taught behavioral techniques, as needed, to assist them in meeting their weight, calorie, and exercise goals.

- **Self-monitoring:** Self-monitoring will consist of recording weight, caloric intake, and/or exercise, using a website or app. depending upon the intervention step (see Tables 1 & 2), participants will be given appropriate self-monitoring targets. Weight monitoring (at least weekly) will be conducted at all levels of intervention.
- **Feedback:** Participants will be taught to use weight, calorie and/or exercise monitoring as an ongoing source of feedback. A major role of the interventionist will be to monitor and evaluate the progress of participants and provide positive reinforcement for behavior changes. The interventionist will encourage small steps toward behavior change and will elicit personalized behavioral goals.
- **Goal setting:** The interventionist will engage the participant in goal setting to achieve the behavioral goals (i.e., caloric intake, exercise) likely to realize the GWG recommendations and PPWL goals. They will also identify their personal reasons for striving for healthy GWG and/or PPWL as a strategy to develop and maintain motivation.
- **Problem solving:** Participants will be taught to use problem solving strategies to deal with situations that pose difficulties for changing their eating and exercise habits (e.g., vacations, spouse deployment, work stress).

**Meal replacements:** Meal replacements appropriate for pregnant and postpartum women will be offered to those women at the highest “step” or intensity of the interventions, as a method to achieve their weight and calorie goals as well as a strategy to control portions. With an eye toward sustainability, we will use commercially-available meal replacements (e.g., Slim Fast, Better Oats oatmeal, Healthy Choice frozen meals), like we have in our ongoing Fit Blue trial (FWH20130095H) at Lackland AFB. Meal replacements will be purchased through food vouchers and through actual food provided (e.g., oatmeal packets) and given, at no-cost, to participants who are struggling the most in their gestational weight gain or postpartum weight loss (step 3 of the intervention, after they have not met goals for two sessions in a row). The food vouchers and actual food will differ in value, depending on the size of the food item (e.g., a 10-pack of oatmeal that is expected to last 5 days). However, we will spend approximately \$3.00 for two meal replacements per day for these participants. These are not considered gifts nor a form of compensation, and are part of the treatment, for those who are struggling with the weight goals the most.

Participants will be encouraged to replace 2 meals with meal replacements and will be advised to consume a third meal of conventional foods. We will select meal replacements that meet the nutritional needs of pregnant and postpartum women and will provide detailed meal plans that recommend conventional foods to be consumed, to ensure a balanced diet appropriate for pregnant and postpartum women. They will be advised to use the meal plans as guidance for their third conventional meal or for all meals, if they refuse meal replacements at any point. [name], as a registered dietician, will guide the meal replacement choices and the Look AHEAD meal plan adaptation.

- **Toolbox:** The toolbox will include additional treatment options (e.g., providing exercise videos, lower calorie cookbooks, arranging a session with an exercise physiologist/trainer) for participants who need assistance in meeting weight, calorie or exercise goals, or coping with challenges in meeting these goals. The toolbox items are not considered a form of compensation, and will be returned to the research team.
- **Additional behavioral strategies:** As appropriate, the interventionist will introduce other behavioral strategies using adapted Look AHEAD ILI lessons on topics such as stimulus control, social support, and combating negative thinking.
- **Trained Interventionists with Military Knowledge:** A critical part of any military intervention is the ability of the interventionist to understand the culture and the language of the participants. A sentence like, “I just got my PCS orders and have to go to the CSS to start paperwork, which will require an OPR that my OIC wants by COB Friday, but first I have to take my fitness test,” is the norm. To civilians, this appears to be gibberish, but all military personnel know these acronyms because they are part of everyday life. Interventionist credibility is extremely important and if the interventionist does not understand the common vernacular of an active duty member, they lose credibility. We have addressed this with our research staff by ensuring that we have retired military staff available to educate and answer any questions our non-military staff might have, and we strive to retain our trained interventionists across research projects. Our interventionists have Bachelor’s or Master’s degrees in applicable areas (i.e., social work, counseling/psychology, child development, and nursing). As a result, we have highly trained interventionists who are very familiar with military culture and experienced in delivering behavioral interventions. An interventionist will be paired with a participant at randomization and will continue working with the participant throughout the entire intervention, to facilitate social support.
- **Treatment Fidelity:** Based on our previous experience with behavioral interventions, we will utilize the following quality procedures to help ensure treatment fidelity: 1) detailed intervention protocol development; 2) careful interventionist proficiency and ongoing re-training; 3) recording of 10% of intervention sessions to provide corrective feedback on protocol adherence; 4) electronic documentation of all intervention contacts in the study database to monitor participant exposure to

treatment; and 5) weekly study meetings to review participants' adherence to structured protocols (based on the process data collected). These study meetings (attended by all interventionists and investigators) will also include problem solving related to challenging cases and refining skills.

